## 6.17. Subject Withdrawal

Subjects may withdraw from the study at any time at their own request, or they may be withdrawn at any time at the discretion of the investigator or sponsor for safety, behavioral, or administrative reasons. Events to consider could include but are not limited to:

- Adverse events.
- Intercurrent illness.
- Loss to follow-up.

Note: All reasonable efforts must be made to locate subjects to determine and report their ongoing status. This includes follow-up with persons authorized by the subject as noted above. Lost to follow-up is defined by the inability to reach the subject after a minimum of three documented phone calls, faxes, or emails as well as lack of response by subject to one registered mail letter. All attempts should be documented in the subject's medical records. If it is determined that the subject has died, the site will use permissible local methods to obtain the date and cause of death. If investigator's use of third-party representative to assist in the follow-up portion of the study has been included in the subject's informed consent, then the investigator may use a Sponsor retained third-party representative to assist site staff with obtaining subject's contact information or other public vital status data necessary to complete the follow-up portion of the study. The site staff and representative will consult publicly available sources, such as public health registries and databases, in order to obtain updated contact information. If after all attempts, the subject remains lost to follow-up, then the last known alive date as determined by the investigator should be reported and documented in the subject's medical records.

- Lack of efficacy.
- Pregnancy.
- Non-compliance with study drug, protocol requirements, or study-related procedures.
- Serious eligibility or on-study violations of the protocol (e.g., the subject does not have the disease under study).
- Study termination by Sponsor or regulatory authorities.
- Subject's decision to withdraw/withdrawal of consent.

Note: Subjects who request to discontinue study treatment will remain in the study and must continue to be followed for protocol specified follow-up procedures. The only exception to this is when a subject specifically withdraws consent for any further contact with him/her or persons previously authorized by subject to provide this information. Subjects should notify the investigator of the decision to withdraw

consent from future follow-up in writing, whenever possible. The withdrawal of consent should be explained in detail in the medical records by the investigator, as to whether the withdrawal is from further treatment with study drug only or also from study procedures and/or post treatment study follow-up, and entered on the appropriate CRF page. In the event that vital status (whether the subject is alive or dead) is being measured, publicly available information should be used to determine vital status only as appropriately directed in accordance with local law.

- Investigator discretion in case of occurrence of any medical condition, requirement for prohibited concomitant medication or treatment, or circumstances that would expose the subject to substantial risk and/or would not allow the subject to adhere to protocol requirements.

For subjects who have participated in Study A0081105, subjects must be withdrawn at any time during Study A0081106 if any 1 of the following predetermined subject exit criteria is met:

- An episode of status epilepticus.
- A 28-day PGTC seizure rate during open-label treatment that is greater than 2-times the maximum 28-day study seizure rate during the Study A0081105 baseline phase (a 28-day period is defined as a minimum of 4 consecutive study weeks).

Subjects with any of the following should be discussed with the Pfizer Study Clinician or representative for potential withdrawal:

- An episode of a newly emergent generalized seizure type during open-label treatment compared with the subject's history.
- An increase in the rate or intensity of PGTC or other generalized seizure activity that, according to the investigator, is clinically significant.

Protocol-specified withdrawal procedures are the same as those to be performed at Visit 8 and 9.

**Note:** under certain circumstances, when subjects leave the study early (early termination), dosing with the taper medication may be inadvisable. The decision not to taper the subject is upon agreement from the Sponsor's Study Clinician or Designee. If the taper will not be utilized then all assessments required at Visit 8 should be conducted where possible.

If a subject does not return for a scheduled visit, every effort should be made to contact the subject. In any circumstance, every effort should be made to document subject outcome, if possible. The investigator should inquire about the reason for withdrawal, request the subject to return all unused investigational product(s), request the subject to return for a final visit, if applicable, and follow-up with the subject regarding any unresolved adverse events. If the subject withdraws from the study and also withdraws consent for disclosure of future information, no further evaluations should be performed and no additional data should be

collected. The sponsor may retain and continue to use any data collected before such withdrawal of consent.

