- g. Month 12, Visit 8 is the End of Treatment/End of Study visit for subjects who will not initiate taper of pregabalin per the discretion of the investigator. Visit 8 will be the final study visit for these subjects. For subjects who will taper their pregabalin treatment, Visit 8 is considered End of Treatment/End of Study Visit but they will initiate taper at this visit and return for a follow-up Visit 9 to end taper. For early terminations, all Visit 8 procedures should be performed and if taper is initiated, subjects should return for follow-up Visit 9.
- h. Cogstate Battery will be completed only for pediatric partial onset seizure subjects (Protocol A0081041) 4-16 years of age.
- i. The follow-up visit is only required for subjects who received taper medication.
- j. All screening procedures must be completed prior to administration of first study medication. All eligibility criteria should be confirmed prior to, or on, Visit 2.
- k. Adjust the dose if needed based on seizure response and tolerability.

\* TC = Telephone Contact to assess dosing and diary compliance, concomitant medications, and AE's.

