#### **6.5. Clinic Visit 4 (Month 2/Day 60 ±4 Days)**

The following activities will be performed at Visit 4:

- Review and record adverse events.
- Review and record all concomitant medications and non-drug treatments/procedures.
- Collect and review seizure and dosing diary and record number and type of seizure.
- Adjust the dose if needed based on seizure response and tolerability.
- Complete assessment of suicidal ideation and behavior (C-SSRS or CBCL) using appropriate version or test for subject's age. If CBCL is administered, scores must be obtained as soon as possible. If positive scores are obtained on the CBCL or CSSRS, a mental health risk assessment must be performed by a qualified mental health professional prior to randomization (please refer to [Section 7 - ASSESSMENTS](#)).

- Collect and record vital signs.
- Evaluate and record study medication compliance.
- Dispense study medication via tele-randomization system.
- Dispense subject daily seizure and dosing diary.

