#### **6.7. Clinic Visit 5 (Month 4/Day 120 ±4 Days)**

The following activities will be performed at Visit 5:

- Review and record adverse events.
- Review and record all concomitant medications and non-drug treatments/procedures.
- Collect and review seizure and dosing diary and record number and type of seizure.
- Complete assessment of suicidal ideation and behavior (C-SSRS or CBCL) using appropriate version or test for subject's age. If CBCL is administered, scores must be obtained as soon as possible. If positive scores are obtained on the CBCL or CSSRS, a mental health risk assessment must be performed by a qualified mental health professional prior to randomization (please refer to [Section 7 - ASSESSMENTS](#)).
- Evaluate and record study medication compliance.
- Dispense study medication via tele-randomization system.
- Dispense subject daily seizure and dosing diary.

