#### **6.11. Telephone Contact (Month 8/Day 240 ±4 Days)**

The Investigator (or designee) will contact the parent/subject by telephone to ensure medication compliance and provide guidance for accurate dosing as required.

- Review subject's compliance with dosing regimen.
- Review completion of dosing and seizure diary.
- Review concomitant medications and non-drug treatments/procedures.
- Assess adverse events.

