#### **6.12. Clinic Visit 7 (Month 9/Day 270 ± 4 Days)**

The following activities will be performed at Visit 7:

- Review and record adverse events.
- Review and record all concomitant medications and non-drug treatments/procedures.
- Collect and review seizure and dosing diary and record number and type of seizure.
- Adjust the dose if needed based on seizure response and tolerability.
- Complete assessment of suicidal ideation and behavior (C-SSRS or CBCL) using appropriate version or test for subject's age. If CBCL is administered, scores must be obtained as soon as possible. If positive scores are obtained on the CBCL or CSSRS, a mental health risk assessment must be performed by a qualified mental health professional prior to randomization (please refer to [Section 7 - ASSESSMENTS](#)).
- Evaluate and record study medication compliance.
- Collect urine samples for a urine pregnancy test (for female subjects who are menarchal).
- Collect and record vital signs.
- Dispense study medication via tele-randomization system.
- Dispense subject daily seizure and dosing diary.

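### The mandatory PGTC exit rule needs a 28-day seizure count, but none is scheduled between clinic visits that lie up to 95 days apart (nominal)

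*Protocol*

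**What the plan says.** Protocol 6.17 states that for former A0081105 participants "subjects must be withdrawn at any time during Study A0081106 if any 1 of the following predetermined subject exit criteria is met". One of the two criteria is "A 28-day PGTC seizure rate during open-label treatment that is greater than 2-times the maximum 28-day study seizure rate" of the A0081105 baseline phase, and the section adds that "a 28-day period is defined as a minimum of 4 consecutive study weeks". Other increases in generalized seizure activity are handled differently in the same section: they are discussed with the sponsor's clinician for possible withdrawal.

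Seizures are written in a daily home diary by number and type (Protocol 7.5). The site reads that diary at clinic visits. Protocol 6.12 (Visit 7) is typical: "Collect and review seizure and dosing diary and record number and type of seizure". The same task is listed in 6.3 to 6.5, 6.7, 6.9, 6.15 and 6.16, that is, Visits 2 to 9.

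Between visits there are six telephone contacts, at Months 3, 5, 7, 8, 10 and 11 (6.6, 6.8, 6.10, 6.11, 6.13, 6.14). On the seizure diary, 6.11 lists only "Review completion of dosing and seizure diary". Each call also reviews dosing compliance and concomitant medication and assesses adverse events. The Schedule of Activities summarizes: "TC = Telephone Contact to assess dosing and diary compliance, concomitant medications, and AE's".

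**The concern.** The exit criterion is mandatory and numerical, and it concerns subjects whose convulsive seizures have more than doubled against their own worst baseline rate. A site that follows every call procedure exactly has no number to compare with the threshold until the next clinic visit. Neither document says who calculates the exit-rule rate, when, or from what data between visits.

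Withdrawal dates, and the time on treatment after the criterion is met, would then depend partly on visit spacing. The spacing is widest in the second half of the year, and this is a study of long-term safety. There is no data monitoring committee (Protocol 9.5) that might notice the pattern from outside.

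**Working it through.** The documents give no detection delay, so there is no stated figure to reproduce. Everything below follows from the scheduled days.

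**Inputs.** Clinic visits fall on Days 8 (±1), 30, 60, 120, 180 and 270 (each ±4) and 365 (±7). Calls fall on Days 90, 150, 210, 240, 300 and 330 (each ±4). Sources are the Schedule of Activities and Protocol 6.3 to 6.15. The assessment window is at least 28 days (6.17), so the criterion can first be met on Day 28.

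**1. Gaps between scheduled counts.** Gap = next visit day − this visit day. The maximum adds both windows; for Visit 7 to Visit 8 this is 95 + 4 + 7 = 106. The longest wait from meeting the rule to the next count is gap − 1 if the 28-day window may straddle the visit, and gap − 28 if it must lie wholly after it. Figures are days, nominal (maximum with windows).

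| Interval | Gap | Longest wait, rolling window | Longest wait, window wholly after visit |
|---|---|---|---|
| Visit 3 to 4 | 30 (38) | 29 (37) | 2 (10) |
| Visit 4 to 5 | 60 (68) | 59 (67) | 32 (40) |
| Visit 5 to 6 | 60 (68) | 59 (67) | 32 (40) |
| Visit 6 to 7 | 90 (98) | 89 (97) | 62 (70) |
| Visit 7 to 8 | 95 (106) | 94 (105) | 67 (78) |

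If windows must end on a study-week boundary, the first such day after Day 270 is Day 273, and the longest wait to Day 365 is 92 days.

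**2. Mean wait.** Assume that the day the rule is first met is uniform over Days 28 to 365, that every rolling 28-day window is checked at each reading, and that no other route reveals the increase. For intervals of length L, mean wait = Σ(L²/2) / ΣL.

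- Clinic visits only, L = 2, 30, 60, 60, 90, 95: ΣL = 337 and ΣL² = 4 + 900 + 3,600 + 3,600 + 8,100 + 9,025 = 25,229. Mean = 12,614.5 / 337 = 37.4 days; longest interval 95.
- Clinic visits plus existing calls, L = 2, ten intervals of 30, and 35: ΣL = 337 and ΣL² = 4 + 9,000 + 1,225 = 10,229. Mean = 5,114.5 / 337 = 15.2 days; longest interval 35 (46 with windows).

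**3. Is the SAP rate a backstop?** SAP 6.2.3 divides all seizures since the last visit by the diary days since the last visit and scales to 28. Take, as an illustration, one 28-day burst at k times the baseline maximum, with the baseline maximum on the other 67 of 95 days. The interval rate is (28k + 67) / 95 times the maximum.

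- k = 2.5: (70 + 67) / 95 = 1.44
- k = 4: (112 + 67) / 95 = 1.88

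Both stay below 2, although the 28-day criterion was met. On this pattern the interval rate reaches 2 only at k = (190 − 67) / 28 = 4.39. The SAP also derives no exit-criterion variable.

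**The case against.** A reader might go further and infer that the calls check nothing but diary completion, that the site would never learn of the crossing, or that the rule cannot be applied at all. The documents do not support any of these.

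- Every call also assesses adverse events and concomitant medication. Protocol 8.3 counts worsening of the underlying disease as a possible adverse event, and 8.13 has every subject questioned about adverse events. The medication review may bring out as-needed benzodiazepine use for seizure exacerbation (5.5) or changes in antiepileptic drugs (5.4.1).
- Section 6 allows a subject to be seen at any time for safety, and 6.17 separately sends clinically significant increases to the sponsor's clinician without any count.
- Because the diary is daily, any past 28-day window can be rebuilt at the next clinic visit. The rule is applied late, not lost.

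It is also fair to say that the timing phrase in 6.17 can mean whenever in the study the criterion is met, without promising continuous surveillance. Seizure data are summarized descriptively, so no inference is at risk, and only former A0081105 subjects are affected. The Schedule of Activities (footnote b) carries data over from the earlier study, so the baseline maximum may already be obtainable at the site.

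These points make a long undetected delay less likely. They do not close the gap, because each route depends on someone volunteering or judging a worsening, and none yields the number that a mandatory numerical criterion requires.

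**Conclusion.** The point holds as a gap between a stated rule and the schedule that feeds it. No seizure count is scheduled between clinic visits, so the criterion can be met up to about 3 months before the next scheduled count: 94 days nominal with a rolling window, or 67 if the window must start after the visit.

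That is a worst case, reached only if neither the family nor the adverse-event question raises the increase. The 37-day mean should not be read as an expected delay. It rests on a uniform crossing day and no other detection, and the documents establish neither. Its use is the comparison with about 15 days under the same assumptions when the existing calls also read the count.

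The correction is worth making because it is cheap and serves a safety criterion that the protocol already treats as mandatory.

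**What to change.** Reconcile Protocol 6.17 with 6.6, 6.8, 6.10, 6.11, 6.13, 6.14 and the telephone-contact row of the Schedule of Activities:

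- At each existing call, record the number, type and dates of seizures from the diary since the last contact.
- For former A0081105 subjects, check every 28-day window ending since the last contact against the criterion already in 6.17. Checking only the latest four weeks would miss a window that crossed and ended between contacts, and would not deliver the 15-day mean and 35-day maximum. Dates are needed so that windows spanning two contacts can be built.
- State that each A0081105 subject's maximum baseline 28-day rate is available at the site from Visit 1A.

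The threshold and the withdrawal rule stay as they are. The cost is slightly longer calls, one transcribed number per PGTC subject and a short amendment. No new visits are needed.

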## 7. ASSESSMENTS

Every effort should be made to ensure that the protocol required tests and procedures are completed as described. However it is anticipated that from time to time there may be circumstances outside of the control of the investigator that may make it unfeasible to perform the test (eg, a subject may not be able or willing to comply due to neurological compromise, motor deficits or cognitive impairment). In these cases if an assessment cannot be performed the investigator will take all steps necessary to ensure the safety and well being of the subject. This may include gathering assessment data from a parent or legally acceptable representative who may answer assessment questions on behalf of the subject based upon their knowledge and observations of the subject. When a protocol required assessment cannot be performed the investigator will document the reason for this and any corrective and preventive actions which he/she has taken to ensure that normal processes are adhered to as soon as possible, if feasible.

### 7.1. Physical and Neurological Examination

A physical examination will be performed and must be completed by a Medical Doctor (MD), Doctor of Osteopathy (DO), Nurse Practitioner (NP) or Physician Assistant (PA) or appropriate equivalent based upon normative country-specific practices.

Full physical and neurological exams will be performed at Visits 1A and 1B. An abbreviated physical exam and full neurological exam will be performed at Visit 6 and 8 (i.e., at the completion of the study or early termination).

Physical examinations will evaluate the following body systems/organs: general appearance; dermatological; head and eyes; ears, nose, mouth, and throat; pulmonary; cardiovascular; abdominal; genitourinary (optional); lymphatic; musculoskeletal/extremities. For pediatric subjects Tanner Stage will also be assessed at screening (Visit 1A or 1B) and at completion/early termination (Visit 8).

Neurological exam will assess: level of consciousness, mental status, cranial nerve assessment, muscle strength and tone, reflexes, pin prick and vibratory sensation (the latter using a 128-Hz tuning fork), coordination and gait.

Any clinically significant changes from the entry physical or neurological examinations will be recorded as adverse events. A physical and neurological exam will be performed at the screening and at the completion of study visit or early termination.

### 7.2. Vital Signs, Height and Weight

Sitting blood pressure and pulse are to be recorded at the Screening Visit (Visit 1A or 1B), Visits 4, 6, 7 and at the completion of the study. Height (using stadiometer when appropriate) will also be recorded at the Screening Visit (Visit 1A or 1B), Visit 6 and at the

completion of the study. Weight will be recorded at Visits 1A or 1B, 6, and 8. Weight recorded at Visit 1A or 1B and Visit 6 will be used to calculate the dose for subsequent visits.

